**Background**

In 2014, the Danish Government introduced a new school policy requiring an average of 45 minutes physical activity (PA) daily during the school day. The overall objective of this natural experiment is to examine the effectiveness of this national school policy on objectively-measured PA levels among Danish school-aged children aged 6 – 17 years between 2009 – 2018 (1). PA was measured by accelerometry during a 7-day period in children from 31 schools in 2017-2018 (post-policy) and compared to data from four historical school-based studies conducted between 2009-2012 (pre-policy) (2-5). All invited schools in the post-policy

population were represented in the pre-policy study populations, and calendar periods of data collection and age groups were matched according to the four historical studies.

#### **Aims:**

- *The primary aim* is to examine the effectiveness of the 2014 school policy on school time PA, which is defined by any bodily movement above sitting and standing.
- *The secondary aims* are to examine the effectiveness of the 2014 school policy on
  - o School time moderate to vigorous PA (MVPA) and total PA (mean counts per minute (CPM))
  - o Overall (school- and leisure time) PA, MVPA and mean CPM

#### **Data processing and statistical analyses**

##### *Accelerometry*

PA was assessed by waist-mounted accelerometry. The device was mounted with an elastic belt. In the four pre-policy studies ActiGraph monitors (AM7164, GT1M, and GT3X) were used. In the post-policy study, Axivity AX3 accelerometers were used. The Axivity AX3 instrument stores raw acceleration, whereas the main output of Actigraph monitors is counts per time unit. A newly developed aggregation method enables the generation of Actigraph counts from raw acceleration with very high agreement (6), which enables harmonization of PA data across different instruments. Data were processed using 10-seconds epochs.

Since timetables were not available in all pre-policy studies, aggregated acceleration data by age group and study were used to create PA intensity trajectories for each weekday represented. In these, a clear pattern appeared during the school hours due to the constant shift between class and recess. The trajectories made it possible to identify a group level *morning wake time, evening to bedtime and start and end of school day*. Subsequently, these time points were used to define: i) school time and ii) total time (from morning till bedtime). The time point identification was done by two researchers separately and then compared to ensure data quality. Moreover, the time points were compared to timetables available in the post-policy population.

PA levels will be examined from 2009-2018. During the same period, it is anticipated that the length of the school day has expanded due to the 2014 school policy, which will influence the total school time participants have available to accumulate PA. As a supplement, a standardized 8.10am-1pm school time variable was conducted, which controls the effect of school length. Both the standardized school time variable and the school time variable based on the above-mentioned trajectories will be used to examine the primary aim.

i) School- and ii) total PA will be examined using following PA outcomes:

- *Time spent with PA above 753 CPM* is the primary outcome of this study. The school policy does not specify the intensity of the 45 minutes of daily PA required. Thus, a new cut-off point is generated with the assumption that PA is any bodily movement above sitting and standing. In the post-policy population, participants wore an Axivity accelerometer around the waist and thigh (only waist is used in the present study). A new method using the thigh-worn accelerometer is with high accuracy able to objectively classify different activity types (7). Thus, the >753 cut point was determined by using the thigh accelerometer classification to extract the activity counts measured at the hip for sitting and walking activities, and subsequently a ROC analysis was carried out to estimate the threshold that distinguish walking from sitting with the highest possible sensitivity (0,908) and specificity (0,899) (data not published).
- *Time spent with MVPA* using the Evenson cut-point (>2296 CPM) is a secondary outcome (8)
- *Mean CPM* as a general measure of total volume of PA is a secondary outcome

#### *Statistical analyses*

All analyses will be conducted in StataBE 17 (StataCorp).

All outcomes are continuous. Thus, a linear mixed-effect model approach will be used to examine any changes in PA levels over time. Time will be treated as a categorical variable in which each year (2009, 2010, 2012 and 2017/18) represents a category. A newly published Danish report based on objective data from the post-policy population reports differences in PA levels among boys and girls and different age-groups during school time (9), and analyses will therefore be adjusted for age and gender. Moreover, analyses will be adjusted for seasonal variations (10). Project, school-identifier and individual identifier will be modelled as random effects due to the assumption that observations within these clusters are not independent, and individual identifiers are nested in schools, which are nested in projects. We assume that the effect of the school policy might be different in the younger school children compared to the older ones. Thus, an interaction term or stratification will be utilized to account for this.

Initially, pre-policy trends ( $t$ : 2009, 2010 and 2012) will be inspected.  $t$  denotes time ( $t=2009, 2010, 2012, 2017/18$ ) and  $b(t)$  denotes reference-category contrasts describing the effect of time  $t$  with  $t=2009$  as reference category. Firstly, we will test pre-policy linearity in  $b(t)$  ( $H_0: b(2010)=b(2012)/3$ ). If linearity exists, we will test for a constant pre-policy level in  $b(t)$  ( $H_0: b(2010)=b(2012)=0$ ). If the pre-policy trend is either

linear (positive or negative) or constant, we will analyze post-policy data using mixed-effect linear regression testing either i) whether linearity (positive or negative) continues post-policy ( $H_0: b(2010) = b(2012)/3 = b(2017/18)/8.5$ ) or ii) no difference between pre- and post-policy, if the pre-policy trend is constant ( $H_0: b(2010)=b(2012)=b(2017/18)=0$ ). This will be examined using post-estimation testing of linear combinations of coefficients. If no linear trend exists in pre-policy data, a bootstrap method will be implemented testing whether  $b(2017/18)$  significantly exceed any pre-policy estimates in  $b(2009)$ ,  $b(2010)$  or  $b(2012)$ . If using the bootstrap method, we will make no assumptions regarding pre-policy trends in  $b(t)$ .

Data will be checked for all statistical assumptions concerning the mixed-effect model; normality and homoscedasticity of residuals and linearity between dependent and independent variables.

Analyses are completed in February and March 2022.

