#### **Codebook:**

Variable name	Variable Label	Variables types	Legal values	Value labels
id_project	Individual and project identifier	Categorical/nominal		
gender	Boy or girl	Categorical/dichotomous	0, 1	0: Girl, 1: Boy
age	Age at examination	Continuous	6-18	
school_level	School level at examination	Categorical/dichotomous	1, 2	1: 0th-5th grade, 2: 6 th -9th grade
grade	Academic school year	Categorical/ordinal	1-9	1: grade 1, 2: grade 2 etc.
school_at_examination	School at examination	Categorical/nominal	1-57	1: school 1, 2: school 2 etc.
year	The year of data collection	Categorical/nominal	2009, 2010, 2012, 2017/18	2009, 2010, 2012, 2017/18
season	The season of data collection	Categorical/dichotomous	1, 2	1: spring/summer, 2: fall/winter
project2	Project over time - FASER matched with historical projects	Categorical/nominal	1-4	1: CHAMPS, 2: EYHS, 3: NBBB, 4: SPACE
Intervention	Pre- or post-intervention	Categorical/dichotomous	0, 1	0: Pre-intervention, 1: Post-intervention
category	The day is divided in 4 categories (events)	Categorical/nominal	1- 5	1: school time (timetable), 2: school time (standard 8.10-13), 3: Leisure time, 4: Total (full day)
Duration	Duration of events in minutes (categories above)	Continuous		
Weekday	Day of the week	Categorical/nominal	1-5	1: mon, 2: tue, 3: wed, 4: thur 5: fri

DayNumber	Day of recording	Categorical/nominal	1-8	1: First measurement day, 2: Second... etc.
non-wear	Minutes of non-wear	Continuous		
Cpm	Average counts per minutes	Continuous		
mvpa_min	Minutes of moderat to vigorous physical activity (>2296 counts)	Continuous		
movement_min	Minutes of movement (>753 counts)	Continuous		

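### The linear trend tests take gaps of 1, 3 and 8.5 years from calendar-year labels; if seasonal mix or post-policy timing differs between year categories, a steady trend can look like a departure

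*SAP*

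**What the plan says.** In the SAP's section on statistical analyses, time enters the mixed model by label: "Time will be treated as a categorical variable in which each year (2009, 2010, 2012 and 2017/18) represents a category". The year effects b(t) are contrasts against 2009, adjusted for age, gender and season.

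Pre-policy linearity is tested as "H_0: b(2010)=b(2012)/3". If the trend is judged linear but not constant, the post-policy test is "H_0: b(2010) = b(2012)/3 = b(2017/18)/8.5". If it is judged constant, the test sets all year effects to zero. If it is not linear, a bootstrap asks whether 2017/18 exceeds the pre-policy estimates.

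The codebook defines the time variable as "The year of data collection" and has a second variable, "The season of data collection", with two levels: "1: spring/summer, 2: fall/winter". It lists no measurement date or month. The background section says that, for the post-policy study, "calendar periods of data collection and age groups were matched according to the four historical studies". It does not give those periods.

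**The concern.** The two linear hypotheses are true under a steady trend only if the season-adjusted time gaps behind b(2010), b(2012) and b(2017/18) stand in the ratio 1 : 3 : 8.5. Nothing in the SAP shows that they do. With four studies in three pre-policy categories, the spring/fall mix may differ between categories. The post-policy wave is given one value, 8.5, however its recordings divide between 2017 and 2018.

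Two decisions depend on this. The first hypothesis chooses between the linear and bootstrap branches. These ask different questions: the bootstrap compares 2017/18 with pre-policy levels, so after a wrong rejection of linearity a steady rise with no policy effect could still exceed them. The second hypothesis is the policy test in the linear branch. Because it extrapolates from 2012, an error in the 2012 gap is multiplied by 8.5/3 = 2.83.

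**Working it through.** **The plan's own figures.** 2010 − 2009 = 1; 2012 − 2009 = 3; (2017 + 2018)/2 − 2009 = 8.5. The divisors reproduce exactly as label differences.

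**Error under a linear trend.** Let activity change by s per year with no policy effect, and let g1, g2, g3 be the gaps that the fitted year effects actually represent. Then b(2010) = s·g1, b(2012) = s·g2 and b(2017/18) = s·g3, so

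- linearity contrast: b(2010) − b(2012)/3 = s(g1 − g2/3)
- post-policy departure: b(2017/18) − (8.5/3)·b(2012) = s(g3 − 2.83·g2)

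Both should be 0.

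**Assumed layouts.** The SAP gives no dates, so these are illustrations: spring at 0.25 and fall at 0.75 of the year, equal numbers per category, no noise, least squares with year category and two-level season. A true seasonal effect on activity would be absorbed by the season term and would not change the results.

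| Layout | g1, g2, g3 | Linearity | Departure |
|---|---|---|---|
| A. Spring share 20%, 80%, 50% in 2009, 2010, 2012; post-policy a quarter each in spring and fall of 2017 and 2018 | 1, 3, 8.5 | 0 | 0 |
| B. Pre-policy as A; post-policy half fall 2017, half spring 2018 | 0.817, 2.909, 8.409 | −0.15s | +0.17s |
| C. 2009 fall only; 2010 and 2012 spring only; post-policy as B | 0, 2, 8 | −0.67s | +2.33s |
| D. 2009 and 2010 spring only; 2012 fall only; post-policy as B | 1, 4, 9 | −0.33s | −2.33s |
| E. All pre-policy in spring; post-policy 99% spring 2018, 1% fall 2017 | 1, 3, 9 | 0 | +0.50s |
| F. Half spring, half fall in every pre-policy year; post-policy as B | 1, 3, 8.5 | 0 | 0 |

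**Layout C by hand.** Only the post-policy wave contains both seasons, so it alone fixes the season coefficient: fall minus spring = 2017.75 − 2018.25 = −0.5 years. The 2009 fall records become, on the spring scale, 2009.75 + 0.5 = 2010.25. Hence g1 = 2010.25 − 2010.25 = 0, g2 = 2012.25 − 2010.25 = 2, g3 = 2018.25 − 2010.25 = 8. Contrasts: 0 − 2/3 = −0.67 and 8 − (8.5/3)·2 = +2.33.

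**Layout D by hand.** 2012.75 + 0.5 = 2013.25, so g2 = 4 and g3 = 2018.25 − 2009.25 = 9. Contrasts: 1 − 4/3 = −0.33 and 9 − (8.5/3)·4 = −2.33.

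**Why season adjustment does not settle it.** Within one calendar year, spring precedes fall by 0.5. In a wave running from fall 2017 to spring 2018 the order is reversed. One season coefficient cannot fit both, and the misfit passes into b(t) when the seasonal mix differs between categories. In C the raw mean-date gaps are 0.5, 2.5 and 8.25, giving 0.5 − 2.5/3 = −0.33 and 8.25 − (8.5/3)·2.5 = +1.17; the season term doubles both.

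**Why raw mean-date gaps are not the remedy.** In A the labels are exact, but the raw gaps are 0.70, 2.85 and 8.35. Using these as divisors gives 1 − 3·0.70/2.85 = +0.26s and 8.5 − 3·8.35/2.85 = −0.29s, errors where there were none. In C they leave 0 − 2·0.5/2.5 = −0.40s and 8 − 2·8.25/2.5 = +1.40s.

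**The case against.** A reader might infer that the waves were in fact measured at different times of year by study, and so that 1, 3 and 8.5 are wrong. The SAP does not support this. It gives no measurement month for any study; a two-level season variable and matched calendar periods show only that timing could differ. In layouts A and F the season-adjusted gaps are exactly those in the plan. This stands: the gaps are undocumented, not shown to be false.

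It also stands that the error scales with an unknown slope and disappears at zero slope, so the constant-level hypotheses, which use no spacings, are untouched. The SAP gives no slope, standard error or significance level, so no false-rejection rate for this study can be computed.

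The matching of calendar periods is a weaker defence. It ties the post-policy study to the historical ones. It does not align 2009, 2010 and 2012 with each other, and it does not say how recordings divide between 2017 and 2018. Layout E shows that identical pre-policy timing is not enough for the post-policy test. The season term is not a general defence either, as B to E show.

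**Conclusion.** The point holds in limited form. The linear hypotheses rest on label gaps that the SAP does not justify, and under plausible timing an exactly linear, non-zero trend with no policy effect would violate one or both of them.

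In the assumed layouts the absolute error runs from 0 to about 0.67s for linearity and from 0 to about 2.3s for the post-policy departure. For illustration, at an assumed slope of 1 minute per year that is at most about 0.7 and 2.3 minutes. The upper values need years measured in a single season; with both seasons in every category (B) the errors are about 0.15s and 0.17s.

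Whether this matters depends on the standard errors. At an assumed two-sided 5% level, a spurious single contrast of 1, 2 or 3 standard errors would be rejected with probability 0.17, 0.52 or 0.85. It would go too far to say that the trend tests are invalid: the true gaps may be close to 1, 3 and 8.5. The point is worth correcting because the check is cheap and the linear branch's policy conclusion depends on it.

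**What to change.** Fit the planned model (year category, season, the other covariates and any interaction) with decimal measurement date as the outcome, keeping the random-effects weighting of the activity model. Take its year coefficients as d1, d2 and d3. Test b(2010)/d1 = b(2012)/d2, then b(2010)/d1 = b(2012)/d2 = b(2017/18)/d3, and report d1 to d3. Write the tests in cross-multiplied form, d2·b(2010) = d1·b(2012) and d2·b(2017/18) = d3·b(2012), because d1 can be zero, as in layout C. If the analysis is stratified, derive the divisors in each stratum.

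With the same design and weights, these divisors make both contrasts zero under any linear trend, and they return 1, 3 and 8.5 where the labels are right. Raw mean-date gaps should not be combined with season-adjusted b(t).

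The cost is small: measurement dates must be retrieved from the recordings, if retained, since the codebook does not list them; one auxiliary fit is needed per analysis; and the divisors are no longer round numbers. No new data collection is needed.

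### Weekday is in the dataset and shaped the school-hours definition, yet the day-level model omits it; adding it costs four coefficients and protects the year effects if weekday mix varies by year

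*SAP*

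**What the plan says.** Under Statistical analyses, the SAP fits a linear mixed model with year as a categorical term (2009 as reference). On covariates it says that "analyses will therefore be adjusted for age and gender", followed by "Moreover, analyses will be adjusted for seasonal variations". On clustering it says "Project, school-identifier and individual identifier will be modelled as random effects". An interaction or stratification separates younger from older pupils. No weekday or day term is listed.

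Under Accelerometry, school start and end were identified at group level, because timetables were missing in some pre-policy studies: "aggregated acceleration data by age group and study were used to create PA intensity trajectories for each weekday represented". A second, fixed 8.10am–1pm school window is also defined, and both school-time variables serve the primary aim.

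The Codebook lists a variable labelled "Day of the week", coded "1: mon, 2: tue, 3: wed, 4: thur 5: fri", and a day-of-recording variable running from 1 to 8, coded "1: First measurement day, 2: Second... etc".

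The Background gives a 7-day measurement period and says that calendar periods and age groups were matched to the historical studies. It does not mention weekday.

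**The concern.** The codebook and the individual random effect together imply several day records per child. The primary outcome is minutes above a threshold within school time. The SAP itself notes that a longer school day gives more time to accumulate activity. If school length or activity varies across the week, a year with relatively more records from a low-activity weekday will have a lower mean for that reason alone.

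The year effects carry the whole evaluation: the pre-policy trend tests and the policy contrast are both built on b(t). The comparison joins four separate historical studies to one later study, so differences in fieldwork, such as hand-out day or days kept after non-wear, can line up with year. Season is adjusted for; weekday, which is also held in the dataset, is not.

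**Working it through.** The SAP gives no weekday effects, no weekday distribution by year and no figure on this point, so there is nothing to reproduce. Every magnitude below rests on assumed inputs.

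**Formula.** Without a weekday term, the bias in a year contrast is approximately

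bias in b(t) = Σ over weekdays of (share in year t − share in 2009) × weekday effect.

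If the shares are equal, this is zero whatever the weekday effects are.

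**Illustrative range.** Suppose one weekday differs by 10–20 minutes and its share differs by 5–10 percentage points between years:

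- low end: 0.05 × 10 = 0.5 min
- high end: 0.10 × 20 = 2.0 min

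**Finer grid.** One weekday is lower by d minutes and makes up 20% of records in 2017/18. Bias = −(0.20 − 2009 share) × d:

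| 2009 share | d = 5 | d = 10 | d = 15 |
|---|---|---|---|
| 20% | 0 | 0 | 0 |
| 18% | −0.1 | −0.2 | −0.3 |
| 15% | −0.25 | −0.5 | −0.75 |
| 10% | −0.5 | −1.0 | −1.5 |
| 0% | −1.0 | −2.0 | −3.0 |

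**Does the child random intercept absorb it?** This was simulated with 20 runs, 500 children per period, a true year effect of 0 and Friday lower by an assumed 10 minutes. The assumed standard deviations were 12 min between children and 15 min within. Mean estimated year effect in minutes:

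| Friday records in the earlier period | No weekday term | With weekday term | Shift |
|---|---|---|---|
| all | +0.26 | +0.26 | 0.00 |
| half | −0.69 | +0.26 | −0.95 |
| none | −1.71 | +0.22 | −1.93 |

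The Monte Carlo standard error is about 0.15–0.18, so the common offset near +0.25 is within two standard errors of zero. The shifts are close to the formula. With half the Fridays, the share is 0.5/4.5 = 11.1%, giving −(0.200 − 0.111) × 10 = −0.9. With none, it gives −2.0. The random intercept does not remove the bias; the weekday term does.

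**Would a week of recording guarantee balance?** Seven complete days contain each weekday once. The day-of-recording variable runs to 8, however. Eight consecutive dates starting on a weekday contain that weekday twice: 2 of 6 weekday records (33%), against 1 of 6 (17%) for each other weekday. If all eight days were kept, and one study always started on the low weekday while another never did, the shares would differ by 1/6 = 16.7 points, or 0.167 × 10 = 1.7 min. This is an extreme case. It shows only that balance depends on hand-out day and on which days are retained.

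**The case against.** The strongest reply is that the document contains no error here. The sentence on season is correct, the SAP never promises weekday adjustment, and no imbalance is shown. A complete 7-day recording gives equal shares and zero bias. All of this stands, and it is why the point is minor.

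Several stronger readings are tempting but unsupported:

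- A reader might infer from the weekday-specific curves that some studies lack a weekday. The wording allows this, but it reads equally well as one curve per weekday in the data.
- A reader might infer that curves were drawn by weekday because school length differs across the week. The reason given for using curves is missing timetables; the SAP does not say that length varies by weekday.
- A reader might assume that weekday is complete for every record. The codebook lists the variable without stating completeness.

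The fixed 8.10am–1pm window answers the school-length part for one of the two primary analyses. Weekday differences in activity inside that window remain. The curve-based school-time variable has no such protection. Total time runs from morning to bedtime, so school length does not set its window, but other weekday differences can still enter.

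The assumed imbalance is also not small. Taking one weekday from 20% to 15% or 10% of records, with the others complete, means losing about 29% (1 − 0.706) or 56% (1 − 0.444) of that weekday's records. An 18% share with a 10-minute effect gives only 0.2 min.

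One possible objection does not stand: that weekday adjustment would remove part of the policy effect. The policy does not change which weekdays were measured, and a weekday effect common to all years leaves any lengthening of the school day in b(t).

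**Conclusion.** The omission is real, and its consequence is conditional. The bias in a year contrast is zero if weekday mix is the same across years. It is 0.5–2.0 minutes under the assumed 10–20 minute weekday difference and 5–10 point share difference, and less for the 8.10am–1pm variable. The documents supply neither input.

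A reader might carry the bias through the linear-trend test, where an error in b(2012) is multiplied by 8.5/3 = 2.83 when projected to 2017/18, giving 2.0 × 2.83 = 5.7 minutes. That figure needs the largest assumed weekday effect, the largest assumed imbalance and all of the bias on b(2012). Bias falling on 2017/18 itself is not multiplied. Nothing in the SAP supports that combination, so it should not be quoted as the expected size.

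The point stands as a minor improvement to the model, not as a demonstrated flaw in the results or in the sentence on season.

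**What to change.** Add weekday (five categories) as a categorical fixed effect to all school-time and total-time models. State in the SAP that the model is fitted to day-level records. Report a table of weekday by study year, so that a reader can see whether the adjustment matters.

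The cost is four coefficients, using a variable already in the codebook; no new data are needed. A common weekday effect assumes a similar weekday pattern in all years. If the table shows a marked imbalance, a comparison of the year effects with and without the term would show how much depends on it.

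### If the SAP's project level is project2, its model assumes every school changed equally; where schools changed unequally, the post-policy tests reject too often, and a school-by-year random intercept is needed.

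*SAP*

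**What the plan says.** Under Statistical analyses, the SAP plans a linear mixed model with year as a categorical fixed effect, adjusted for age, gender and season. On clustering it says "Project, school-identifier and individual identifier will be modelled as random effects due to the assumption that observations within these clusters are not independent", and that "individual identifiers are nested in schools, which are nested in projects". The only variation in policy effect it allows for is between younger and older children. The model checks cover residual normality, homoscedasticity and linearity.

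The hypotheses are joint tests on the year coefficients. After a linear pre-policy trend, the test is whether that trend continues (2 df). After a constant one, it is whether all years are equal (3 df). On both the SAP says "This will be examined using post-estimation testing of linear combinations of coefficients". If pre-policy linearity is rejected, a bootstrap is used; its resampling unit is not stated.

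The Codebook gives project2 four levels and the label "Project over time - FASER matched with historical projects". School has one variable with legal values 1-57, labelled "1: school 1, 2: school 2 etc". Background says the post-policy data come from "children from 31 schools in 2017-2018 (post-policy"), and that all invited schools in the post-policy "population were represented in the pre-policy study populations".

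**The concern.** With project2 as the top level, a school measured before and after the policy keeps one random effect. That effect largely cancels from the pre/post contrast, so the model treats the contrast as if only child-level noise remained. This is right only if every school moved by the same amount.

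The SAP's own text gives reason for doubt. It notes that the policy leaves intensity open, so schools could meet it differently. It also sets school start and end times by age group and study, so a school whose timetable differs from its group's carries an error shared by all its pupils. Any such school-specific change is a cluster-level error that the planned standard errors omit. The planned model checks would not reveal it.

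At stake are the tests that decide the primary aim. Confidence intervals for 2017/18 would be too narrow and a change would be declared too readily.

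**Working it through.** The SAP gives no alpha, ICC or number of children per school, so there is no figure of its own to reproduce. A nominal 5% is assumed throughout.

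**1. Are school codes shared across periods?** Separate pre and post codes for 31 re-measured schools need at least 31 + 31 = 62 codes. The Codebook has 57, so at least some schools carry one code in both periods.

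**2. Variance of the pre/post contrast.** Set the total child-level variance to 1. Let m be children per school-period and CAC the correlation of a school's effect between periods. School-by-time variance is τ² = ICC × (1 − CAC); residual variance is σ² = 1 − ICC. For a school seen twice, the true variance of its difference is 2(τ² + σ²/m), while the planned model uses about 2σ²/m. The ratio is 1 + mτ²/σ².

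- Mild corner (m = 30, ICC 0.05, CAC 0.9): τ² = 0.005; ratio 1 + 30 × 0.005/0.95 = 1.158; SE ratio 1.08; size 2{1 − Φ(1.96/1.076)} = 6.9%.
- Upper corner (m = 50, ICC 0.10, CAC 0.8): τ² = 0.02; ratio 1 + 50 × 0.02/0.90 = 2.111; SE ratio 1.45; size 2{1 − Φ(1.96/1.453)} = 17.7%.

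**3. Simulation of the SAP's tests.** There were 20,000 datasets per setting, with 57 schools of which 31 were re-measured, one pre-policy year per school (57 + 31 = 88 school-periods), all true year effects zero, and no covariates. Two splits of schools over 2009/2010/2012 were used. Monte Carlo error is about ±0.3 points at 5% and ±0.6 at 25%. Ranges run over m = 30 or 50 and ICC 0.05 or 0.10, with CAC 0.8 or 0.9 unless stated.

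| Model | 2-df linear | 3-df constant | 2017/18 vs pre-policy mean |
|---|---|---|---|
| Planned, project2 reading | 6.6-19.4% | 7.2-25.5% | 6.6-18.0% |
| Planned, CAC = 1 | 4.9-5.6% | 4.9-5.6% | 4.9-5.6% |
| Added school-by-time intercept, REML, Satterthwaite df | 4.9-6.0% | 4.8-5.8% | 4.5-5.4% |
| Post-policy study as its own project level | 5.0-5.8% | 3.0-4.0% | 0.4-2.1% |

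A separate, smaller run gave about 17% (2-df) and 25% (3-df) at the upper corner and about 5-6% at the mild corner. The lower end is therefore close to harmless.

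**4. If schools have several pre-policy years.** The SAP does not say that each school was measured in only one. Suppose about a third were measured in all three, at the upper corner (600 datasets; error about 1.96 × √(0.19 × 0.81/600) = ±3 points at 19%).

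- Planned model: 22.3% (2-df) and 26.2% (3-df).
- A school-by-period intercept still leaves 18.5% on both.
- A school-by-year intercept gives 5.5% and 5.2%.
- Gates fitted to pre-policy data alone reject in 15.3% (linearity) and 20.7% (constant). With one pre-policy year per school they reject in 5.3-5.8% and 5.4-6.3%.

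**5. Four projects.** With a project intercept fitted and a true project variance of 0.01 of child variance, the added term leaves 7.2-8.2% on the two joint tests, against 11.5-30.0% for the planned model (one pre-policy year per school).

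**6. Bootstrap branch.** For pairwise differences between 2017/18 and an earlier year, true SE over bootstrap SE is 1.13-1.56 when children are resampled within schools and 1.02-1.10 when whole schools are resampled. The SAP's rule of exceeding any pre-policy estimate was not simulated.

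**The case against.** The strongest reply is that two conditions must both hold and the SAP settles neither.

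**Which variable is project.** The text never names it, and the Codebook also has id_project, which identifies individual and project together. A reader might infer that 57 codes against 62 proves the project2 reading. It does not: if schools were nested in a separate post-policy project, a shared code would still yield separate effects per period, and the contrast would become conservative. This stands as a limit. project2 remains the better-supported reading, because it is the only stand-alone project variable and is built to span time. A separate post-policy level would also coincide with the 2017/18 category. Either way the SAP has to say which it is.

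**Whether schools changed unequally.** Nothing in the SAP measures this, and every percentage rests on assumed inputs. The simulation also has no covariates. The planned age interaction could absorb age-related differences in school change, and stratification would leave fewer children per school-period where schools span both age groups. Either would reduce the inflation. This stands too: the direction follows from the algebra, but the size is only illustrative.

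**Random effects need not mean intercepts only.** That is so; the SAP neither states nor excludes a random slope. But it lists three levels and no term letting schools differ over time, and intercepts are the ordinary reading.

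**Conclusion.** The point holds conditionally. If project is project2 and schools changed by different amounts, the 2017/18 standard errors are too small and the 2-df and 3-df tests reject too often: about 7-19% and 7-26% over the assumed range with one pre-policy year per school. With zero school-by-time variance the planned model is valid.

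Three stronger readings are not supported. A reader might infer that the planned tests are invalid as they stand; the SAP shows no unequal change, and under the other project reading this inflation is absent. A reader might infer that the pre-policy gates are safe if fitted to pre-policy data alone, as "2009, 2010 and 2012) will be inspected" can be read; that holds only if each school was measured in one pre-policy year. A reader might infer that any pre/post school term cures the problem; a school-by-period term does not when schools have several pre-policy years.

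This is worth fixing because the tests decide the primary aim and the remedy is cheap. Confidence is medium, since the variance inputs are assumed.

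**What to change.** - Name the variable used as the project level, and say whether schools contributed to more than one pre-policy year.
- Add a school-by-year random intercept between school and individual. It is the same model as school-by-period when each school has one pre-policy year, and it remains adequate when schools have several.
- Fit by REML with a small-sample degrees-of-freedom correction.
- State whether the pre-policy gates are tested in the four-year model or on pre-policy data alone.
- In the bootstrap branch, resample whole schools. This reduces the problem but does not fully remove it.

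The cost is one random-effects level and a few sentences, with no new data. Confidence intervals widen: in the simulation with one pre-policy year per school, the SE of the 2017/18 contrast is 4-5% larger if the added variance is zero, and 8-42% larger over the assumed range where it is not. The term does not cure having only four projects.
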